**Figure 1 Study flow chart**

Revised Clinical Study Protocol  
Drug Substance AZD5069  
Study Code D3550C00002  
Edition Number 1  
Date

**Table 3**                      **Table of study assessments**

Study Visit	Visit 1	Visit 1.1	Visit 2	Visit 2.1	Visit 3	Visit 4	Visit 5	Visit 6	Visit 7
Time (No. weeks/days)	Prior to Visit 1.1	14 – 21d prior to V2	Day 0	Day 2	1 week	2 weeks	3 weeks	4 weeks	3-18d after V6
Detail	Consent	Screening	Start treatment	Interim treatment visit	Interim treatment visit	Interim treatment visit	Interim treatment visit	End of treatment visit	Follow up
Written informed consent a	✓								
Demographics		✓							
Medical & surgical history		✓							
COPD history		✓							
Smoking history		✓							
Height		✓							
Weight		✓	✓					✓	✓
Concomitant medication		✓	✓	✓	✓	✓	✓	✓	✓
Inclusion/exclusion criteria	✓ b	✓ b	✓ b,d						
Physical examination c		✓	✓ d		✓	✓	✓	✓	✓
Vital signs		✓	✓ d		✓	✓	✓	✓	✓
Body temperature e		✓	✓ d		✓	✓	✓	✓	✓
Safety bloods (haematology (excluding leucocyte count) & clinical chemistry (including CRP))		✓ f	✓ d,f		✓ f	✓ f	✓ f	✓ f	✓ f
Urinalysis g		✓	✓ d		✓	✓	✓	✓	✓
LH and FSH (blood) h		✓							
Urine pregnancy test i		✓	✓ d						✓
12 Lead ECG		✓	✓ d	✓				✓	✓
Spirometry j		✓	✓ d		✓	✓	✓	✓	✓
Randomisation			✓						

**Table 3 Table of study assessments**

Study Visit	Visit 1	Visit 1.1	Visit 2	Visit 2.1	Visit 3	Visit 4	Visit 5	Visit 6	Visit 7
Time (No. weeks/days)	Prior to Visit 1.1	14 – 21d prior to V2	Day 0	Day 2	1 week	2 weeks	3 weeks	4 weeks	3-18d after V6
Detail	Consent	Screening	Start treatment	Interim treatment visit	Interim treatment visit	Interim treatment visit	Interim treatment visit	End of treatment visit	Follow up
PK blood sampling			✓ k1			✓ k1	✓ k	✓ k1	
Leucocyte count including circulating neutrophils m		✓	✓ k1	✓	✓	✓ k1	✓ k	✓ k1	✓
Administer morning dose of investigational product in clinic (only applicable for PK sub study)			✓			✓ n		✓ n	
Dispense study drug			✓						
Drug accountability					✓	✓	✓	✓	
Blood sample for biomarkers			✓ d					✓	
Archive blood sample			✓ d					✓	
Adverse Event Questioning		✓	✓	✓	✓	✓	✓	✓	✓
Blood sample for Pharmacogenetics			✓ o						
Diary p	✓	→							
Telephone contact q					✓	✓	✓	✓	✓

a Informed consent must be obtained prior to any study-related procedures, restrictions or screening assessments. Adequate time must be given between consent and screening according to local requirements

b Inclusion and exclusion criteria to be assessed at applicable visits (where relevant at V1, V1.1 and V2)

c At Visits 1.1, 6 and 7 a full physical examination is require, at other visits a more brief examination is sufficient (see Section 6.4.6)

d Pre-dose assessments

e As well as body temperature measured at clinic visits, patients will be provided with an accurate thermometer and should record their oral body temperature twice daily (morning and evening) in their daily diary. Patient-recorded oral body temperature measurements will not be entered into the WBDC system. Patients will be instructed by site staff to contact the clinic if their body temperature increases above 38.1°C and this should be reported as an AE (see Section 6.4).

f Haematology analysis at the central laboratory will include leucocyte (and neutrophil) counts as exploratory variables at Visits 1.1, 2, 3, 4, 5, 6 and 7. Each single sample will be repeated analysed at the central laboratory (Quintiles); the first analysis will be upon receipt of the sample and then repeat

Revised Clinical Study Protocol  
 Drug Substance AZD5069  
 Study Code D3550C00002  
 Edition Number 1  
 Date

analysis at twice daily time intervals eg, at 5.00 pm and 9.00 am until expiry at 72 hours post-sample collection. Exploratory leucocyte measurements taken at the central laboratory are for internal modelling use only and will not be reported in the CSR. Central laboratory leucocyte measurements will also only be available at the end of the study so as not to compromise the study blind.

The following will be assessed as part of the urinalysis dipstick: glucose, protein, blood. In addition, samples will be sent to the central laboratory for urine microscopy and quantitative measurements of total protein, albumin and creatinine if the local dipstick test for protein and/or blood is positive or if the urine sample appears abnormal on macroscopic examination, eg, if it is cloudy

Only for women under 50 years old, to confirm post-menopausal status

All women

Spirometry (lung function assessments) will be performed at the same time of day throughout the study  $\pm$ 2 hours relative to the time at baseline (Visit 2) pre- and 30 minutes post-bronchodilator

On PK days (Visits 2, 4, 5 and 6), blood samples for assessment of plasma PK and circulating leucocytes (including neutrophils) will be collected as far apart as possible (minimum of 90 minutes between samples) and patients should continue to take investigational product as per their normal schedule. Date and time of dose will be recorded in the electronic Case Report Form (eCRF) for Visit 2 and the first PK/leucocyte samples will be collected pre-dose. At Visit 3, 4, 5 and 6 the date and time of dosing on the clinic day and on the previous 2 days will be recorded in the eCRF.

Approximately 16 patients, at selected sites, will complete a PK sub-study. The patients will follow the same visit schedule as the main study but 3 of the clinic visits (Visits 2, 4 and 6) will be extended and the patient will remain at site for approximately 5 hours. Patients must not take investigational product (AZD5069 or placebo) at home on the morning of Visits 4 and 6. At these extended visits, 5 blood samples (pre-dose and then at approximately 1, 2, 3 and 5 hours post-dose) will be drawn for evaluation of plasma PK and blood samples (to match PK samples taken pre-dose [Visit 2 only], 1 and 3 hours post-dose) will be drawn for measurement of circulating leucocytes (including neutrophils). Further details can be found in Section 6.6

Circulating leucocytes counts (including neutrophils) will be analysed at a local laboratory within 2 hours (maximum 4 hours) of sample draw as circulating neutrophils deteriorate rapidly after blood has been taken. In the main study, on PK days, leucocyte counts will be assessed in blood collected at the same time as AZD5069 concentration. In the PK sub-study, 3 leucocyte samples will be taken at Visit 2 and 2 leucocyte samples will be taken at each of Visits 4 and 6 to match the PK samples taken pre-dose (Visit 2 only), 1 and 3 hours post-dose. The leucocyte results from Visit 2-7 (inclusive) will be blinded from the site staff, refer to Section 5.4.1

Patients taking part in the PK sub-study should take their morning dose of study drug (AZD5069 or placebo) in the clinic after pre-dose assessments have been completed

Optional blood sample for retrospective pharmacogenetic exploratory analysis to be taken at Visit 2 or any subsequent visit after randomisation providing the patient has provided separate consent for the pharmacogenetics part of the study

Patients will complete a daily diary card recording date and time of dosing, fasting status, use of concomitant medication, oral body temperature twice daily and any changes in the medical state of the patient. A new diary card will be given to the patient at each clinic visit. The patient should bring their completed diary card to each of their clinic visits for review and discussion with clinical staff. Data on diary cards will not be entered into the eCRF directly but information will be reviewed with clinical staff to enable them to record date and time of dose on selected days in the eCRF and support accurate recording of compliance, concomitant medication and AEs in the medical records and eCRF.

Clinic staff will contact patients twice weekly via telephone in order to monitor any AEs, assess general health status, ensure that the patients are without fever and to ascertain whether an additional clinic visit is required.

## 3.2 Rationale for study design, doses and control groups

The study is being conducted in moderate to severe COPD patients as this is the target population for the study drug. The rationale for the optional pharmacogenetics component of the study is included in Appendix D.

### 3.2.1 Patient population and control groups

The patient population will be males and females of non-childbearing potential aged between 40-80 years (inclusive) with a clinical diagnosis of COPD, with symptoms for more than 1 year prior to Visit 1.1. The patients must be current or previous smokers with a smoking history of at least 10 pack years and have an FEV1  $\geq$ 30% and  $<$ 80% of predicted normal value and an FEV1/FVC  $<$ 70% (both post-bronchodilator) at Visit 1.1.

### 3.2.2 Study design

The study will be randomised, placebo-controlled and double-blind to ensure a robust design and minimise bias, which could compromise the conduct of the study, the recording of data and/or interpretation of the results. As the leucocyte count (including neutrophil data) will potentially be unblinding to site and study personnel, the data will be blinded from Visit 2 to Visit 7. The study includes placebo in parallel with active investigational product doses, to limit the occurrence of conscious and unconscious bias in the conduct of the trial and interpretation of the data. Randomisation will be stratified for use of inhaled corticosteroids and dynamic randomisation methodology will be applied to minimise imbalance across treatment groups.

### 3.2.3 Selection of outcome variables

The end-points chosen as primary variables are those that will assess the safety and tolerability of AZD5069 50 mg and 80 mg, bd in COPD patients.

The end-points chosen as secondary variables are those that will assess the AZD5069 concentration in plasma in COPD patients and the relationship between AZD5069 exposure and circulating neutrophils and will assist in future dose selection.

### 3.2.4 Dose consideration and treatment duration

Two doses of AZD5069, 50 mg and 80 mg, bd, will be administered to COPD patients for 4 weeks.

These doses have been selected based upon established safety and tolerability in the GSAD and GMAD studies, and have been chosen to minimise the risk that patients will have drops in circulating neutrophils below  $1.0 \times 10^9/L$  for periods longer than 24 hours.

Following 100 mg bd dosing in the GMAD, 1 out of 6 healthy subjects had neutrophil counts which decreased below  $1.0 \times 10^9/L$ . Based on the PK/PD modelling done from the GSAD data, on 80 mg bd, 15% or less of the healthy subjects dosed would be expected to experience a neutrophil decrease below this limit that persists for more than 24 hours. Therefore this dose was chosen to be near the top of the dose response curve based on systemic neutrophil

decrease, where the large majority of COPD patients (whose neutrophil numbers will be elevated in comparison with healthy volunteers) would be expected to complete 1 month's dosing. 50 mg is a dose where no patients would be expected to withdraw due to decreases in neutrophils, according to the withdrawal criteria.

A treatment period of 4 weeks has been selected as this is considered sufficient to investigate safety and tolerability and will be supported with respect to toxicology.

## 4. PATIENT SELECTION CRITERIA

Investigator(s) should keep a record, the patient screening log, of patients who entered pre-study screening.

Each patient should meet all of the inclusion criteria and none of the exclusion criteria for this study. Under no circumstances can there be exceptions to this rule.

### 4.1 Inclusion criteria

For inclusion in the study patients should fulfil the following criteria:

1. Provision of informed consent prior to any study-specific procedures
2. Male, or female of non-childbearing potential ie, women who are permanently or surgically sterilised or post menopausal.

Women will be considered post menopausal if they are:

- (i) under 50 years of age and have been amenorrhoeic for 12 months or more following cessation of exogenous hormonal treatments and with luteinizing hormone (LH) and follicle stimulating hormone (FSH) levels in the post-menopausal range

or

- (ii) over 50 years old and have been amenorrhoeic for 12 months or more following cessation of all exogenous hormonal treatments

Permanent sterilization is defined as having undergone hysterectomy and/or bilateral oophorectomy and/or bilateral salpingectomy; bilateral tubal occlusion on its own is not adequate

3. Aged 40 – 80 years inclusive at screening (Visit 1.1)
4.  $FEV_1 \geq 30\%$  and  $< 80\%$  of the predicted normal value post-bronchodilator as assessed at screening (Visit 1.1)

5. FEV1/FVC <70% post-bronchodilator at screening (Visit 1.1)
6. Current or ex-smokers with a smoking history of ≥10 pack years (1 pack year = tobacco consumption corresponding to 20 cigarettes smoked per day for one year) at screening (Visit 1.1)
7. Documented clinical diagnosis of COPD, GOLD stage II - III (according to Global Initiative on Obstructive Lung Disease (GOLD) guidelines) with symptoms for more than 1 year before Visit 1.1
8. COPD patients on a stable treatment regimen, as judged by the Investigator
9. Body mass index (BMI) of 18-30 kg/m^2 (inclusive) and a weight of 50-100 kg (inclusive).

Criteria relating specifically to the optional pharmacogenetics component can be found in Appendix D.

## 4.2 Exclusion criteria

Patients should not enter the study if any of the following exclusion criteria are fulfilled:

1. Any clinically significant disease or disorder (eg, cardiovascular, gastrointestinal, liver, renal, neurological, musculoskeletal, endocrine, metabolic, psychiatric, major physical impairment) which, in the opinion of the investigator, may either put the patient at risk because of participation in the study, or may influence the absorption, distribution, metabolism and excretion of drugs
2. Patients with active or latent tuberculosis (TB)
3. Patients with known Human Immunodeficiency Virus (HIV) or who belong to a high-risk group for HIV infection
4. Evidence of serum hepatitis or presence of hepatitis B surface antigen or hepatitis C antibodies
5. Patients with other latent or chronic infections (eg, recurrent sinusitis, urinary tract infection) or at risk of infection (surgery, trauma, significant infection within 90 days before Visit 2, history of skin abscesses or soft tissue infection within 90 days before Visit 2 or, in the opinion of the investigator, patients in regular contact with subjects who have active pulmonary TB [[Martineau et al 2007](#)]).
6. Exacerbation of COPD (defined as worsening in COPD requiring treatment with oral or parenteral antibiotics and/or oral or parenteral glucocorticosteroids (GCS) and/or hospitalization-related) which was not resolved within 30 days of Visit 2

7. Clinically significant lower respiratory tract infection not resolved 4 weeks prior to Visit 2, as judged by the investigator
8. Requirement for long term oxygen therapy
9. Patients who have received live or live-attenuated vaccine in the 2 weeks prior to first dosing (Visit 2)
10. Asthma and any current respiratory tract disorder other than COPD, which is considered by the investigator to be clinically significant or may influence the result of the study
11. Disease history suggesting reduced or abnormal immune function other than that related to COPD
12. Any clinically relevant abnormal findings in physical examination, clinical chemistry, haematology, urinalysis, vital signs or ECG at baseline (Visit 1.1), which, in the opinion of the investigator, may either put the patient at risk because of participation in the study, or may influence the results of the study, or the patient's ability to participate in the study
13. Active malignancy or neoplastic disease in the previous 12 months
14. Alanine aminotransferase (ALT) / aspartate aminotransferase (AST) level  $\geq 1.5$  x upper limit of normal (ULN) at screening (Visit 1.1)
15. Neutrophil count below the lower limit of normal (LLN)
16. Abnormal crystals in the urine at Visit 1.1 (if dipstick test for protein and/or blood is positive or if the urine sample appears abnormal on macroscopic examination)
17. Patients who have had a clinically significant illness within 4 weeks before Visit 2 as determined by the investigator
18. Blood donation of more than 500 mL during the previous 12 weeks before Visit 2 and more than 50 mL in the 2 weeks before Visit 2
19. Known or suspected hypersensitivity to the investigational product or any excipients or a compound of the same class
20. Current evidence of drug abuse or significant history of drug abuse as judged by the investigator
21. Current evidence of alcohol abuse or significant history of alcohol abuse as judged by the investigator

22. Participation (defined as administration of at least one dose of an investigational product) in another clinical study within 12 weeks preceding Visit 2
23. Patients who, in the opinion of the investigator, should not participate in the study
24. Previous exposure to AZD5069
25. Scheduled inpatient surgery or hospitalisation during the study
26. Pregnancy or breast-feeding during the study
27. Involvement in the planning and/or conduct of the study (applies to both AstraZeneca staff and/or staff at the study site)
28. Previous randomisation in the present study
29. Use of oral or systemic glucocorticosteroids within 30 days prior to Visit 2
30. Concomitant immunosuppressive medication
31. Use of prohibited medications (see [Table 6](#))
32. Patients with serum creatinine, above the upper limit of the reference range at screening (Visit 1.1)

Criteria relating specifically to the optional pharmacogenetics component can be found in Appendix D.

Procedures for withdrawal of incorrectly enrolled patients see Section [5.3](#).

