### **Outcome variable(s):**

Primary variable:

- Safety and tolerability variables
  - Adverse Events (AEs)
  - 12-lead Electrocardiogram (ECG)
  - Physical examination
  - Haematology, clinical chemistry and urinalysis

- Vital signs and body temperature
- Pre- and post-bronchodilator lung function tests (Forced Expiratory Volume in 1 second (FEV1), Forced Vital Capacity (FVC), Slow Vital Capacity (SVC), Inspiratory Capacity (IC), Forced Expiratory Flow 25-75% (FEF25-75%))

Secondary variables:

- Pharmacokinetic variables
  - AZD5069 concentration in plasma and resulting PK parameters
- Pharmacodynamic variable
  - Circulating neutrophil count in blood

Exploratory variables:

- Safety variables
  - Neutrophil counts determined at different times post-sample collection
- Pharmacokinetic variables:
  - Potential future pharmacokinetic and metabolic investigations
- Pharmacodynamic variables:
  - Blood inflammatory biomarkers, including, but not limited to sVCAM-1, sICAM-1, CRP, SAA and VEGF
  - Potential future retrospective biomarker investigations of mediators relevant to the mechanism of inflammation in COPD
- Pharmacogenetic- please refer to Appendix D of the Clinical Study Protocol for further details
- To undertake additional analyses of AZD5069 plasma concentrations and / or exposure versus the safety and clinical parameters, if warranted.

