## 7. BIOLOGICAL SAMPLING PROCEDURES

### 7.1 Volume of blood

The total volume of blood that will be drawn from each patient in this study is as follows:

**Table 8** Volume of blood to be drawn from each patient

Assessment		Sample volume (mL)	No. of samples	Total volume (mL)
Safety	Clinical chemistry (including LH and FSH at Visit 1.1)	5	7	35
	Haematology	2	7	14
Leucocyte count		2	12 main study (13 PK sub-study)	24 (26 PK sub-study)
Pharmacokinetic		4	8 main study (17 PK sub-study)	32 (68 PK sub-study)
Biomarker blood sample		8.5	2	17
Archive sample		8.5	2	17
Pharmacogenetic		9	1	9
Total				148 (186 PK sub-study)

A cannula will be supplied for repeated samples as required and a small volume will be discarded before each sample is taken.

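### Exclusion 18 joins its two blood-donation limits with 'and', so for any patient who keeps to the protocol's own donation ban it never excludes anyone

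*Protocol*

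**What the plan says.** Protocol Section 4.2, item 18, excludes patients for earlier blood donation and words its limits as "more than 500 mL during the previous 12 weeks before Visit 2 and more than 50 mL in the 2 weeks" leading up to that visit. It is a single numbered criterion with two volume limits.

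The lead-in to the list is "Patients should not enter the study if any of the following exclusion criteria are fulfilled". Section 4 adds "Each patient should meet all of the inclusion criteria and none of the exclusion criteria for this study" and "Under no circumstances can there be exceptions to this rule"; Section 5.3 repeats that no exceptions are possible.

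Section 5.1 item 6 is the only other rule on donation. It forbids giving blood during the study and for 12 weeks after it. It is a conduct restriction and not an eligibility criterion, and it sets no volume limit for the time before consent.

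The synopsis lists "Haematology, clinical chemistry and urinalysis" among the primary safety and tolerability variables. Table 7 includes haemoglobin and erythrocytes, and Section 12.2.3 summarises laboratory change from the Visit 2 baseline by treatment group.

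**The concern.** A pre-study donation rule with a long window and a short window normally sets two separate limits: one on total volume, one on recent volume. Joined by 'and', the item is met only when both are exceeded. The 2-week window lies inside the 12-week window, so the 50 mL limit can then never exclude anyone by itself. It only narrows the 500 mL limit.

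At stake is whether an eligibility rule that sites must apply without exception does its job. A patient who has recently given a large volume may still be recovering haemoglobin after Visit 2, and that recovery would appear as on-study change unrelated to treatment. The same patient also gives blood for the study: Table 8 totals 148 mL, or "186 PK sub-study". Those are whole-study volumes that start at Visit 1.1 and include an optional 9 mL pharmacogenetic sample, so they are not all drawn soon after a donation.

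**Working it through.** **Step 1: the logic of item 18.** Let A be a total of more than 500 mL in the 12 weeks before Visit 2, and B be more than 50 mL in the last 2 weeks. The text excludes when A and B both hold. The lead-in's 'any' works between numbered items and does not split A from B. The volumes below are illustrations; the protocol gives no donation data.

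| Weeks 12 to 2 (mL) | Last 2 weeks (mL) | Total (mL) | A | B | As written | With 'or' |
|---|---|---|---|---|---|---|
| 550 | 0 | 550 | yes | no | admitted | excluded |
| 900 | 0 | 900 | yes | no | admitted | excluded |
| 480 | 40 | 520 | yes | no | admitted | excluded |
| 0 | 60 | 60 | no | yes | admitted | excluded |
| 0 | 450 | 450 | no | yes | admitted | excluded |
| 0 | 500 | 500 | no | yes | admitted | excluded |
| 0 | 501 | 501 | yes | yes | excluded | excluded |
| 450 | 60 | 510 | yes | yes | excluded | excluded |
| 450 | 0 | 450 | no | no | admitted | admitted |

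**Step 2: does the donation ban cover the 2-week window?** The run-in lasts 14 to 21 days (synopsis; Table 3 places Visit 1.1 at 14 to 21 days before Visit 2). The stated study duration of 7 to 9 weeks is reproduced only if the run-in is counted:

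- shortest: 2 + 4 + 1 = 7 weeks (run-in, treatment, follow-up)
- longest: 3 + 4 + 2 = 9 weeks
- without the run-in: 4 + 1 = 5 to 4 + 2 = 6 weeks, which does not match

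Section 6.2 places consent at Visit 1, before any restriction applies. Section 5.1 item 1 says expressly that it runs from dosing; item 6 does not. The last 2 weeks before Visit 2 therefore fall inside the study, and Section 5.1 item 6 applies to them.

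**Step 3: put the two rules together.** A compliant patient has 0 mL in the last 2 weeks. B is false, so 'A and B' is false for every value of the 12-week total. The 500 mL limit never operates for compliant patients (table rows with 0 mL in the last 2 weeks). Item 18 can exclude only someone who has broken Section 5.1 item 6, and then only if the total also exceeds 500 mL. A patient whose only donation is 51 to 500 mL in that window has broken the ban but is still not excluded by item 18.

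**Step 4: size.** With about 20 patients per arm, one patient moves an arm's mean change by one-twentieth of that patient's own change. If a donor's haemoglobin recovered by an assumed 5 to 15 g/L, the arm mean would shift by 5/20 = 0.25 to 15/20 = 0.75 g/L.

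**The case against.** The best reply is that sites will read item 18 as two limits anyway. Exclusion 10 in the same list uses 'and' loosely to join alternatives. Exclusion 12 (relevant abnormal haematology at Visit 1.1) and exclusion 23 (investigator opinion) give some cover. This has weight, but both backstops depend on judgement, and exclusion 12 cannot see a donation made after Visit 1.1. The same list also shows that the drafters write 'and/or' when either condition is enough, as in exclusion 16: "if dipstick test for protein and/or blood is positive". With about 16 sites and a no-exceptions rule, the wording should not need a charitable reading.

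A second reply is that 'or' does not remove every recovering donor: 450 or 500 mL given 15 days before Visit 2 would still pass. That is true. The change restores the limits the protocol chose; it does not tighten them.

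A reader might infer that the protocol freely lets in patients who donated days before Visit 2. It does not support that: Section 5.1 item 6 forbids such donations. What remains is that breaching the ban does not in itself make the patient ineligible under item 18.

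A reader might also infer that a donor or two would distort an arm's haemoglobin results. The documents give no donor frequency, haemoglobin shift or standard deviation to support this. Allocation is randomised with placebo control and no hypothesis test is planned, so the expected consequence is slight noise and not a difference between arms.

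**Conclusion.** Item 18 is wrong as written, with low impact. Read with Section 5.1 item 6, it excludes no compliant patient, whatever was donated between about 12 and 2 weeks before Visit 2, and it does not exclude a non-compliant patient whose 12-week total is 500 mL or less.

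This rests on two readings. First, the study in Section 5.1 item 6 includes the run-in, which the duration arithmetic and Section 6.2 support. If it were read as starting at Visit 2, the gap would be wider, because a donation in the last 2 weeks would then not be barred either. Second, the two limits were meant to be separate. The protocol does not say so. It is inferred because a joint rule leaves the 12-week limit without effect for compliant patients.

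The number of patients affected is not given and is probably small.

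**What to change.** In Section 4.2 item 18, replace 'and' with 'or', so that exceeding either limit excludes the patient. In the same edit, align it with Section 5.1 item 6: state that the donation ban runs from consent, and how the 50 mL limit relates to a ban that allows no volume at all. If the sponsor did intend a joint condition, it should say so expressly and explain what the 12-week limit is for.

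The cost is one word and a clarifying sentence in the next amendment, and a few donors deferred or excluded. In return, sites apply one rule, haematology change from baseline carries slightly less noise, and fewer patients have study blood drawn soon after a large donation.
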